10.3.3. Recording and Follow-Up of AE and/or SAE**AE and SAE Recording**

- When an AE/SAE occurs, it is the responsibility of the investigator to review all documentation (e.g., hospital progress notes, laboratory reports, and diagnostics reports) related to the event.
- The investigator will then record all relevant AE/SAE information in the CRF.
- It is **not** acceptable for the investigator to send photocopies of the participant's medical records in lieu of completion of the AE/SAE CRF page.
- There may be instances when copies of medical records for certain cases are requested by Sponsor. In this case, all participant identifiers, with the exception of the participant number, will be redacted on the copies of the medical records before submission to Sponsor.
- The investigator will attempt to establish a diagnosis of the event based on signs, symptoms, and/or other clinical information. Whenever possible, the diagnosis (not the individual signs/symptoms) will be documented as the AE/SAE.

Assessment of Intensity

The investigator will make an assessment of intensity for each AE and SAE reported during the study and assign it to 1 of the following categories:

- Mild: An event that is easily tolerated by the participant, causing minimal discomfort and not interfering with everyday activities.
- Moderate: An event that causes sufficient discomfort and interferes with normal everyday activities.
- Severe: An event that prevents normal everyday activities. An AE that is assessed as severe should not be confused with a SAE. Severe is a category utilized for rating the intensity of an event; and both AEs and SAEs can be assessed as severe.

An event is defined as ‘serious’ when it meets at least 1 of the predefined outcomes as described in the definition of an SAE, NOT when it is rated as severe.

Assessment of Causality

- The investigator is obligated to assess the relationship between study intervention and each occurrence of each AE/SAE.
- A “reasonable possibility” of a relationship conveys that there are facts, evidence, and/or arguments to suggest a causal relationship, rather than a relationship cannot be ruled out.
- The investigator will use clinical judgment to determine the relationship.
- Alternative causes, such as underlying disease(s), concomitant therapy, and other risk factors, as well as the temporal relationship of the event to study intervention administration will be considered and investigated.
- The investigator will also consult the Investigator’s Brochure (IB) and/or Product Information, for marketed products, in his/her assessment.
- For each AE/SAE, the investigator **must** document in the medical notes that he/she has reviewed the AE/SAE and has provided an assessment of causality.
- There may be situations in which an SAE has occurred and the investigator has minimal information to include in the initial report to Sponsor. However, it is very important that the investigator always make an assessment of causality for every event before the initial transmission of the SAE data to Sponsor.
- The investigator may change his/her opinion of causality in light of follow-up information and send a SAE follow-up report with the updated causality assessment.
- The causality assessment is one of the criteria used when determining regulatory reporting requirements.

Follow-up of AEs and SAEs

- The investigator is obligated to perform or arrange for the conduct of supplemental measurements and/or evaluations as medically indicated or as requested by Sponsor to elucidate the nature and/or causality of the AE or SAE as fully as possible. This may include additional laboratory tests or investigations, histopathological examinations, or consultation with other health care professionals.
- New or updated information will be recorded in the originally completed CRF.
- The investigator will submit any updated SAE data to Sponsor within 24 hours of receipt of the information.

10.3.4. Reporting of SAEs**SAE Reporting to Sponsor via an Electronic Data Collection Tool**

- The primary mechanism for reporting an SAE to Sponsor will be the electronic data collection tool.
- If the electronic system is unavailable, then the site will use the paper SAE data collection tool (see next section) in order to report the event within 24 hours.
- The site will enter the SAE data into the electronic system as soon as it becomes available.
- After the study is completed at a given site, the electronic data collection tool will be taken off-line to prevent the entry of new data or changes to existing data.
- If a site receives a report of a new SAE from a study participant or receives updated data on a previously reported SAE after the electronic data collection tool has been taken off-line, then the site can report this information on a paper SAE form (see next section) or to Lilly Medical by telephone.

SAE Reporting to Sponsor or Designee via Paper CRF

- Facsimile transmission of the SAE paper CRF is the preferred method to transmit this information to the Lilly Medical.
- Initial notification via telephone does not replace the need for the investigator to complete and sign the SAE CRF pages within the designated reporting time frames.

10.4. Appendix 4: Contraceptive Guidance and Collection of Pregnancy Information

Definitions:

Woman of Childbearing Potential (WOCBP)

A woman is considered fertile following menarche and until becoming post-menopausal unless permanently sterile (see below).

If fertility is unclear (e.g., amenorrhea in adolescents or athletes) and a menstrual cycle cannot be confirmed before first dose of study intervention, additional evaluation should be considered.

Women in the following categories are not considered WOCBP

1. Premenarchal
2. Premenopausal female with 1 of the following:
 - Documented hysterectomy
 - Documented bilateral salpingectomy
 - Documented bilateral oophorectomy

For individuals with permanent infertility due to an alternate medical cause other than the above, (e.g., mullerian agenesis, androgen insensitivity), investigator discretion should be applied to determining study entry.

Note: Documentation can come from the site personnel's: review of the participant's medical records, medical examination, or medical history interview.

3. Postmenopausal female is defined as, women with:
 - i. A woman at least 40 years of age with an intact uterus, not on hormone therapy, who has cessation of menses for at least 1 year without an alternative medical cause, AND a follicle-stimulating hormone >40 mIU/mL; or
 - ii. A woman 55 or older not on hormone therapy, who has had at least 12 months of spontaneous amenorrhea; or
 - iii. A woman at least 55 years of age with a diagnosis of menopause prior to starting hormone replacement therapy.

The investigator will attempt to collect pregnancy information on any male participant's female partner who becomes pregnant while the male participant is in this study. This applies only to male participants who receive study intervention.

After obtaining the necessary signed informed consent from the pregnant female partner directly, the investigator will record pregnancy information on the appropriate form and submit it to the sponsor within 24 hours of learning of the partner's pregnancy. The female partner will also be followed to determine the outcome of the pregnancy. Information on the status of the mother and child will be forwarded to the sponsor. Generally, the follow-up will be no longer than 6 to 8 weeks following the estimated delivery date. Any termination of the pregnancy will be reported regardless of fetal status (presence or absence of anomalies) or indication for the procedure.

Female Participants who become pregnant

The investigator will collect pregnancy information on any female participant who becomes pregnant while participating in this study. The initial information will be recorded on the appropriate form and submitted to the sponsor within 24 hours of learning of a participant's pregnancy.

The participant will be followed to determine the outcome of the pregnancy. The investigator will collect follow-up information on the participant and the neonate and the information will be forwarded to the sponsor. Generally, follow-up will not be required for longer than 6 to 8 weeks beyond the estimated delivery date. Any termination of pregnancy will be reported, regardless of fetal status (presence or absence of anomalies) or indication for the procedure.

While pregnancy itself is not considered to be an AE or SAE, any pregnancy complication or elective termination of a pregnancy for medical reasons will be reported as an AE or SAE.

A spontaneous abortion (occurring at <22 weeks gestational age) or still birth (occurring at >22 weeks gestational age) is always considered to be an SAE and will be reported as such.

Any post-study pregnancy related SAE considered reasonably related to the study intervention by the investigator will be reported to the sponsor as described in Section 8.3.4. While the investigator is not obligated to actively seek this information in former study participants, he or she may learn of an SAE through spontaneous reporting.

Any female participant who becomes pregnant while participating in the study will discontinue study intervention or be withdrawn from the study.

10.5. Appendix 5: Liver Safety: Suggested Actions and Follow-up Assessments

Hepatic Monitoring Tests

Hepatic Hematology^a

Hemoglobin
 Hematocrit
 RBC
 WBC
 Neutrophils, segmented
 Lymphocytes
 Monocytes
 Eosinophils
 Basophils
 Platelets

Hepatic Chemistry^a

Total bilirubin
 Direct bilirubin
 Alkaline phosphatase
 ALT
 AST
 GGT
 CPK

Haptoglobin^a

Hepatic Coagulation^a

Prothrombin Time
 Prothrombin Time, INR

Hepatic Serologies^{a,b}

Hepatitis A antibody, total
 Hepatitis A antibody, IgM
 Hepatitis B surface antigen
 Hepatitis B surface antibody
 Hepatitis B Core antibody
 Hepatitis C antibody
 Hepatitis E antibody, IgG
 Hepatitis E antibody, IgM

Anti-nuclear antibody^a

Alkaline Phosphatase Isoenzymes^a

Anti-smooth muscle antibody (or anti-actin antibody)^a

Abbreviations: ALT = alanine aminotransferase; AST = aspartate aminotransferase; CPK = creatinine phosphokinase; GGT = gamma-glutamyl transferase; Ig = immunoglobulin; INR = international normalised ratio; RBC = red blood cells; WBC = white blood cells.

^a Assayed by Sponsor-designated or local laboratory.

^b Reflex/confirmation dependent on regulatory requirements and/or testing availability.

10.6. Appendix 6: New York Heart Association Cardiac Disease Classification

Functional Capacity

Class I

Study participants with cardiac disease but without resulting limitation of physical activity. Ordinary physical activity does not cause undue fatigue, palpitation, dyspnea, or anginal pain.

Class II

Study participants with cardiac disease resulting in slight limitation of physical activity. They are comfortable at rest. Ordinary physical activity results in fatigue, palpitation, dyspnea, or anginal pain.

Class III

Study participants with cardiac disease resulting in marked limitation of physical activity. They are comfortable at rest. Less than ordinary activity causes fatigue, palpitation, dyspnea, or anginal pain.

Class IV

Study participants with cardiac disease resulting in inability to carry on any physical activity without discomfort. Symptoms of heart failure or the anginal syndrome may be present even at rest. If any physical activity is undertaken, discomfort increases

1994 Revisions to Classification of Functional Capacity and Objective Assessment of Patients with Diseases of the Heart

Reprinted with permission

www.americanheart.org

© 2011, American Heart Association, Inc.

10.7. Appendix 7: Genetics

Use/Analysis of DNA

Genetic variation may impact a participant's response to study intervention, susceptibility to, and severity and progression of disease. Variable response to study intervention may be due to genetic determinants that impact drug absorption, distribution, metabolism, and excretion; mechanism of action of the drug; disease etiology; and/or molecular subtype of the disease being treated. Therefore, where local regulations and IRB/IEC allow, a blood sample will be collected for DNA analysis from consenting participants.

DNA samples will be used for research related to study intervention or T2DM and related diseases. They may also be used to develop tests/assays including diagnostic tests related to study intervention and/or interventions of this drug class and T2DM. Genetic research may consist of the analysis of one or more candidate genes or the analysis of genetic markers throughout the genome or analysis of the entire genome (as appropriate).

The samples may be analyzed as part of a multi-study assessment of genetic factors involved in the response to study intervention or study interventions of this class to understand study disease or related conditions.

The results of genetic analyses may be reported in the clinical study report (CSR) or in a separate study summary.

The sponsor will store the DNA samples in a secure storage space with adequate measures to protect confidentiality.

The samples will be retained as described in Section [10.1.11](#).

10.8. Appendix 8: Dosing Guidance for LY3209590 and Insulin Degludec

10.8.1. LY3209590 Algorithm 1 (paper algorithm)

In Study BDCL, a paper dosing Algorithm 1 will be used by investigators for initiating and adjusting LY3209590 to achieve the target FG ≤ 100 mg/dL (< 5.6 mmol/L).

In situations where study participant safety is a concern, investigators may adjust the dose of LY3209590 recommended by the dose-adjustment algorithm in Table 2; however, clinical rationale must be documented in the eCRF and Lilly Medical must be informed about this deviation and associated medical rationale. If the investigator has safety concerns about the algorithm, the investigator is to contact the Lilly CRP.

At the time of site visit, the investigator will assess the study participant's glycemic control for the previous week and, if necessary, inform the study participant about any needed dose adjustment. The dose will be based on the study participant's FG value from SMBG and hypoglycemia documented in the previous week. Adherence to the dosing algorithm provided for this study is required from Visit 3 (randomization) up to Week 25 and will be monitored periodically by the study team.

General Algorithm Considerations:

- The treat-to-target FG in the algorithm is ≤ 100 mg/dL (< 5.6 mmol/L). LY3209590 dose adjustments will be determined based on the median of the FG from SMBG of at least 3 days (up to 7 days) obtained in the previous week leading up to the visit.
- The LY3209590 dose may not be increased if any SMBG reading was documented at ≤ 70 mg/dL (< 3.9 mmol/L) at any time in the preceding week. Dose decreases of 0.5 mg adjustment may be permitted if multiple episodes of hypoglycemia with SMBG ≤ 70 mg/dL (< 3.9 mmol/L) were recorded, or dose decrease of 1 mg if severe hypoglycemia (requiring assistance) occurred, or if any SMBG was documented at ≤ 54 mg/dL (≤ 3.0 mmol/L) in the preceding week.
- In dosing calculations where rounding is required, round to the nearest 0.25 mg

The initial (Week 0, Visit 3) LY3209590 dose is based on the baseline median fasting glucose and body weight at Visit 3. Because of the long half-life of LY3209590, the change in fasting glucose response following the initial dose may take several weeks to reach desired response; therefore, to minimize the time needed to achieve the desired target glycemic response, the initial dose was **CCI** in order to achieve steady-state concentration within the first week. Directions are provided below to determine the initial dose using Table 1 and for dose adjustments at subsequent visits using Table 2. Examples for Visits 3-6 are provided in *italic text*.

Visit 3 (Randomization Visit):

1. Determine the initial dose by obtaining the participant's body weight and median FG in the week prior to Visit 3 and consulting Table 1.

For example, if a participant weights 83 kg and has a median FG of 185 mg/dl, according to Table 1, the initial dose of LY3209590 is 10.5 mg.

Table 1. Determination of Initial Dose^a of LY3209590 at Visit 3 using Median of Baseline Fasting Glucose and Body Weight

Median Baseline Fasting Glucose (mg/dL)	Median Baseline Fasting Glucose ^b (mmol/L)	Body Weight (kg) at Visit 3			
		≤80	80.1 – 100	100.1 – 120	≥120.1
≤140	≤7.7	3 mg	4.5 mg	6 mg	7.5 mg
141 – 180	7.8 – 10.0	6 mg	7.5 mg	10.5 mg	12 mg
181 – 220	10.1 – 12.2	9 mg	10.5 mg	12 mg	13.5 mg
>220	>12.2	12 mg	13.5 mg	15 mg	16.5 mg

a The initial dose reflects the 3-fold increase needed to reduce the time to target glycemic response and should ONLY be administered once at Visit 3.

b Conversions from mg/dL to mmol/L were rounded off to prevent overlap between threshold ranges and to address that the glucose meter displays 1 significant digit after the decimal when reporting mmol/L readings.

Visit 4 (Week 1)

1. Calculate the total weekly dose LY3209590 mg from the dose administered at Visit 3. (this is **CCI** the dose administered at Visit 3)

*From the Visit 3 example, the LY3209590 total weekly dose is **CCI**.*

2. Use Table 2 to determine the dose adjustment needed for Visit 5 after carefully reviewing participant's fasting glucose (3-7 days prior to visit) and hypoglycemia documented since the last LY3209590 dose.

The participant reported no hypoglycemia since the last dose of LY3209590 and had a median FG of 175 mg/dL. Using the Week 1 (Visit 4) column, the LY3209590 weekly dose should be increased by 3 mg.

3.5 mg + 3 mg = 6.5 mg LY3209590 should be administered at Visit 4.

Table 2. Weekly Dose Adjustment of LY3209590 using the Previous Week's dose (D), Median Fasting Glucose and Hypoglycemic Episodes

Median Fasting Glucose (mg/dL) ^a	Median Fasting Glucose (mmol/L) ^{a,e}	Week 1 (Visit 4) (2 nd dose)	Week 2 (Visit 5) (3 rd dose)	Subsequent Week ^c	
				Dose ≤5 mg	Dose >5 mg
<80 mg/dL or have any nocturnal hypoglycemia or multiple episodes of hypoglycemia ^d	<4.4 mmol/L or have any nocturnal hypoglycemia or multiple episodes of hypoglycemia ^d	D ^b – 1.5 mg	D ^b – 1.5 mg	D ^c – 1.5 mg	D ^c – 2 mg
80 – 100 mg/dL	4.4 – 5.5	D ^b – 1 mg	D ^b – 0.5 mg	No change	No change
101 – 140 mg/dL	5.6 – 7.7	No change	No change	D ^c + 0.25 mg	D ^c + 0.5 mg
141 – 180 mg/dL	7.8 – 10.0	D ^b + 3 mg	D ^b + 1.5 mg	D ^c + 0.5 mg	D ^c + 1 mg
>180 mg/dL	>10.0	D ^b + 5 mg	D ^b + 3 mg	D ^c + 0.75 mg	D ^c + 1.5 mg

- a Based on median fasting glucose from at least 3 fasting glucose from previous week.
- b D for Week 1 (Visit 4) is **CC** of the initial dose from Table 1. D for Week 2 (Visit 5) is Week 1 (Visit 4) dose.
- c LY3209590 dose adjustment starting at Week 3 (Visit 6) will depend on whether previous (Week 2) dose (D) is ≤ 5 mg or > 5 mg and will be adjusted weekly up to Week 12 (Visit 15), then at Week 16 (Visit 17), Week 20 (Visit 18), and Week 24 (Visit 19).
- d The LY3209590 dose may not be increased if any SMBG reading was documented at ≤ 70 mg/dL (< 3.9 mmol/L) at any time in the preceding week. If multiple episodes of hypoglycemia with SMBG ≤ 70 mg/dL (< 3.9 mmol/L) were recorded, follow guidance for dose reduction according to the applicable Visit number. Dose decreases of 1 mg should be made when severe hypoglycemia (requiring assistance) occurred, or if any SMBG was documented at ≤ 54 mg/dL (≤ 3.0 mmol/L) in the preceding week.
- e Conversions from mg/dL to mmol/L were rounded off to prevent overlap between threshold ranges and to address that the glucose meter displays 1 significant digit after the decimal when reporting mmol/L readings.

Visit 5 (Week 2)

1. Confirm the dose of LY3209590 mg administered at Visit 4.

From the Visit 4 example, the LY3209590 weekly dose was 6.5 mg.

2. Use Table 2 to determine the dose adjustment needed for Visit 5 after carefully reviewing participant's fasting glucose (3-7 days prior to visit) and hypoglycemia documented since the last LY3209590 dose.

The participant reported no hypoglycemia since the last dose of LY3209590 and had a median FG of 163 mg/dL. Using the Week 2 (Visit 5) column, the LY3209590 weekly dose should be increased by 1.5 mg.

$6.5 \text{ mg} + 1.5 \text{ mg} = 8.0 \text{ mg}$ LY3209590 should be administered at Visit 5.

Visit 6 (Week 3)

1. Confirm the dose of LY3209590 administered at Visit 5 (Week 2).

From the Visit 5 example, the LY3209590 weekly dose was 8.0 mg.

2. Use Table 2 to determine the dose adjustment needed for Visit 6 after carefully reviewing participant's fasting glucose (3-7 days prior to visit) and hypoglycemia documented since the last LY3209590 dose. Looking at the subsequent week column, apply the prior weekly dose information to the appropriate column (≤ 5 mg or > 5 mg) to obtain the dose increment.

The participant reported no hypoglycemia since the last dose of LY3209590 and had a median FG of 133 mg/dL. Using the Subsequent Week and > 5 mg dose column in Table 2, the LY3209590 dose should be increased by 0.5 mg.

$8.0 + 0.5 = 8.5 \text{ mg}$ of LY3209590 should be administered at Visit 6.

Subsequent visits are managed using the same approach as for Visit 6 (Week 3), always confirming the LY3209590 dose administered at the prior visit, the median fasting glucose during the week prior to the visits, and hypoglycemia status since the last dose of study drug.

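### LY3209590 Algorithm 1 states conflicting dose cuts for overlapping hypoglycemia triggers, and low starting doses can give a negative calculated dose

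*Protocol*

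**What the plan says.** All the dosing text is in Protocol 10.8.1.

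- **General Algorithm Considerations, second bullet.** "Dose decreases of 0.5 mg adjustment may be permitted if multiple episodes of hypoglycemia" with readings at or below 70 mg/dL are recorded. The same bullet gives 1 mg for a severe event or any reading at or below 54 mg/dL.
- **Table 2, first row (row 1 below).** The trigger is "<80 mg/dL or have any nocturnal hypoglycemia or multiple episodes of hypoglycemia". The cut is 1.5 mg at Weeks 1 and 2. From Week 3 it is 1.5 mg if the dose is 5 mg or less, and 2 mg if it is more.
- **Table 2, footnote d, attached to row 1.** For multiple readings at or below 70 mg/dL, sites are to "follow guidance for dose reduction according to the applicable Visit number". It then adds: "Dose decreases of 1 mg should be made when severe hypoglycemia (requiring assistance) occurred", with the same cut for any reading at or below 54 mg/dL.
- **Which text governs later visits.** The paragraph before Table 1 gives directions "for dose adjustments at subsequent visits using Table 2".
- **The dose D to which a cut is applied.** At Visit 4, D is a fraction of the Table 1 starting dose. The fraction is redacted in footnote b. Then "D for Week 2 (Visit 5) is Week 1 (Visit 4) dose".
- **The fraction, recovered.** Table 1 footnote a: "The initial dose reflects the 3-fold increase needed to reduce the time to target glycemic response". The worked example starts at 10.5 mg and continues "3.5 mg + 3 mg = 6.5 mg LY3209590 should be administered at Visit 4". SAP 5.8 also takes one third of the loading dose as the baseline dose.

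The readable text of 10.8.1 has no minimum dose and no rule for a calculated dose of zero or less.

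**The concern.** Protocol 2.3 reports hypoglycemia as the only known insulin risk seen with LY3209590 so far. Protocol 6.1.2.2 sends a participant with a severe event, or with more than one documented episode in a week, to the dosing algorithm for the first reduction. That is where the stated amounts disagree.

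If footnote d is read as the specific rule for severe events, a severe nocturnal event takes off 1 mg, while a mild nocturnal event takes off 1.5 or 2 mg under row 1. The more serious event then gets the smaller cut.

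There is also a reporting consequence. Protocol 10.8.1 requires adherence to the algorithm, and SAP 5.5 counts prescribed doses that did not follow it. Where the algorithm gives two answers, or a negative one, that count has no clear reference dose.

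**Working it through.** **Inputs.** Starting doses from Table 1, cuts from Table 2, and a weekly dose D at Visit 4 equal to the starting dose divided by 3.

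**Reproducing the protocol's example.** 10.5 / 3 = 3.5; 3.5 + 3 = 6.5 (Visit 4); 6.5 + 1.5 = 8.0 (Visit 5); 8.0 + 0.5 = 8.5 mg (Visit 6). All match.

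**The stated cuts side by side.**

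| Situation in the preceding week | General bullet | Footnote d | Row 1 |
|---|---|---|---|
| Multiple readings ≤70 mg/dL | 0.5 mg | refers to the visit-specific cut | 1.5 or 2 mg |
| Severe or ≤54 mg/dL, and also nocturnal, one of several, or median FG <80 mg/dL | 1 mg | 1 mg | 1.5 or 2 mg |
| Single daytime severe event, median FG ≥80 mg/dL | 1 mg | 1 mg | not triggered |

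The first line is a gap of 1 to 1.5 mg between the bullet and the table. The second is a gap of 0.5 to 1 mg inside Table 2 itself. The third shows no conflict.

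**D at Visit 4 (Table 1 / 3, mg), weight bands left to right.**

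| Baseline FG (mg/dL) | ≤80 kg | 80.1–100 kg | 100.1–120 kg | ≥120.1 kg |
|---|---|---|---|---|
| ≤140 | 1 | 1.5 | 2 | 2.5 |
| 141–180 | 2 | 2.5 | 3.5 | 4 |
| 181–220 | 3 | 3.5 | 4 | 4.5 |
| >220 | 4 | 4.5 | 5 | 5.5 |

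**Visit 4.**
- Row 1 (D - 1.5): 1 - 1.5 = -0.5 mg for the 3 mg start; 1.5 - 1.5 = 0 mg for the 4.5 mg start.
- FG 80–100 mg/dL (D - 1), which is within target: 1 - 1 = 0 mg for the 3 mg start, without any hypoglycemia.

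**Two consecutive row 1 weeks (Visits 4 and 5).** Two cells are already at or below zero after Visit 4. Of the rest, D - 1.5 - 1.5 gives:
- 6 mg start (2 cells): 2 - 3 = -1 mg
- 7.5 mg start (2 cells): 2.5 - 3 = -0.5 mg
- 9 mg start (1 cell): 3 - 3 = 0 mg

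That is 2 + 5 = 7 of 16 cells at or below zero: five reach a negative value and two reach exactly zero.

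**What follows a 0 mg week.** Footnote b, read literally, carries D = 0 to Visit 5. Table 2 then gives 0 + 1.5 = 1.5 mg at FG 141–180 mg/dL and 0 + 3 = 3 mg above 180. At FG 101–140 it stays at 0. At FG 80–100 it gives 0 - 0.5 = -0.5 mg. If D = 0 is carried into Week 3, the increments are 0.25, 0.5 or 0.75 mg according to FG. So a zero week still leads to a later dose once glucose rises. A negative result has neither a dose to give nor a usable D to carry.

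**The case against.** The strongest reply is that clinical judgement covers all of this. Final dosing decisions rest with the investigator (Protocol 2.3.1, 4.3, 10.8.1), any reading at or below 70 mg/dL bars an increase, every conflicting rule is still a reduction, the sponsor may modify the algorithm (4.3), and discontinuation follows if reduction is not enough (6.1.2.2). This stands as a limit on harm. It does not tell a site which cut is the algorithm's. Departing from Table 2 is a deviation that must be justified in the eCRF and reported to the sponsor. Section 6.1.2.2 also does not reach a single non-severe nocturnal episode or a result driven by fasting glucose alone, and both can produce a dose of zero or less.

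It is also fair to say that the 0.5 mg clause is leftover wording. It is permissive, and both footnote d and the text before Table 1 point to Table 2. I accept that: the clause should go, and it is not an equal alternative.

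Four stronger readings are tempting, and the documents do not support them:
- **That the plan has no way back after a zero dose.** Footnote b and Table 2 supply one.
- **That 7 of 16 is a share of participants.** It counts table cells. The documents give no distribution over cells and no event frequency.
- **That held weeks use up the 14-day interruption limit in Protocol 7.1.2.** Nothing there says that an algorithm result of zero is an interruption in that sense.
- **That the primary HbA1c result or the hypoglycemia comparison is compromised.** Nothing here shows that.

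**Conclusion.** Protocol 10.8.1 is wrong as written, with modest severity. The three defects are a 0.5 mg clause at odds with the 1.5 or 2 mg in Table 2; no precedence between 1 mg and 1.5 or 2 mg when a severe or ≤54 mg/dL event also meets row 1; and negative calculated doses, at Visit 4 for the 3 mg start and at Visit 5 for the 6 and 7.5 mg starts after two row 1 weeks.

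The arithmetic rests on the factor of one third. It is redacted where it is defined, but the Table 1 footnote, the worked example and SAP 5.8 all give it. The absence of a floor is a statement about the readable protocol only; the Pharmacy Instructions were not available and could set a minimum dose.

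**What to change.** Three edits to Protocol 10.8.1, with amounts confirmed by the sponsor's clinicians:

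1. In the second general bullet, replace both the 0.5 mg and the 1 mg clauses with: *reduce per Table 2 and footnote d*.
2. In footnote d, add: *when more than one rule applies, use the largest single reduction; reductions do not add*. Row 1 (1.5 or 2 mg) then prevails over 1 mg in every overlap of the two.
3. Below Table 2, add: *if the calculated dose is ≤0 mg, give no dose that week and carry D = 0 to the next visit*. The clinicians may set another carried D, but should see its effect. For the 3 mg start, carrying D = 1 mg instead of 0 gives 2.5 mg rather than 1.5 mg at Visit 5 with FG 141–180 mg/dL, possibly soon after hypoglycemia.

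The cost is a protocol amendment, which needs IRB/IEC approval before use (Protocol 10.1.1), and a letter to sites. A participant goes without a dose for a week only where the algorithm already gives zero or less. No extra participants or procedures are needed.
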